7.6.2.1 Hematology

- Hemoglobin, platelets, WBC, neutrophils, RBC, lymphocytes, monocytes, eosinophils, basophils on Durva+Treme: worst CTC grade per patient (**Table 47**)
- Overall hemoglobin, platelets, WBC, neutrophils, RBC, lymphocytes, monocytes, eosinophils, basophils: worst CTC grade per patient (**Table 48**)

7.6.2.2 Serum Chemistry

- Total bilirubin, AST, ALT, alkaline phosphatase, LDH, serum creatinine, chloride, sodium, albumin, potassium, calcium, magnesium, ALP, amylase, lipase, CEA on Durva+Treme: worst CTC grade per patient (**Table 49**)
- Overall total bilirubin, AST, ALT, alkaline phosphatase, LDH, serum creatinine, chloride, sodium, albumin, potassium, calcium, magnesium, ALP, amylase, lipase, CEA: worst CTC grade per patient (**Table 50**)

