5.2 Patient Evaluation Flowsheet: Pre-Treatment, On-Study, and after Protocol Treatment
 For Patients Randomized to Durvalumab and Tremelimumab (Arm 2)

| Required Investigations | PRE-STUDY (≤14 days prior to randomization, unless otherwise indicated) | DURING Protocol Treatment Day 1 each cycle, and as clinically indicated (unless otherwise indicated) | AFTER Protocol Treatment is Permanently Discontinued ¹ | | | |
|---|--|---|---|--------------------------|---|---------------------------|
| | | | PRIOR to objective disease progression | | AFTER objective disease progression | |
| | | | 4 weeks after end of last cycle date | Every 4 weeks thereafter | 4 weeks after end of last cycle date ¹ | Every 12 weeks thereafter |
| History and Physical Exam² | | | | | | |
| Including: height (baseline only), weight, ECOG performance status, clinical tumour measurements (if applicable) | X | X | X | X | X | |
| Vital Signs (blood pressure, heart rate, temperature) | X | X ³ | | | | |
| Concomitant Medications | X | X | X | | X | |
| Overall Survival | | | | | | |
| Survival status assessment | | X | X | X | X | X ⁴ |
| Hematology^{2,5} | | | | | | |
| CBC, differential (including lymphocytes), platelets | X | X ² | X | X | X | X ⁵ |
| Coagulation^{2,5} | | | | | | |
| PTT, PT/INR | X | X ² | X | X | X | X ⁵ |
| Biochemistry^{2,5} | | | | | | |
| Serum Creatinine, Chloride, Sodium, Potassium, Calcium, Magnesium, Bilirubin, ALP, AST and ALT, LDH, Albumin, TSH ⁶ , Amylase, Lipase, Serum CEA | X | X ² | X | X | X | X ⁵ |
| Creatinine Clearance (calculated) | X | as clinically indicated | | | | |
| Glucose | X | as clinically indicated | | | | |
| Radiology⁷ | | | | | | |
| Chest/abdomen/pelvis CT or MRI scan | X ≤ 28 days | X ⁷ Every 8 weeks from randomization until objective disease progression (maintain schedule even if cycles are delayed) | | | | |
| Other scans as necessary to document all measurable and non-measurable disease | X ≤ 28 days | | | | | |
| Other Investigations | | | | | | |
| Pregnancy Test ⁸ | X | | | | | |
| ECG | X | as clinically indicated | | | | |
| Dipstick Urinalysis (including protein, specific gravity, glucose and blood) | X | | | | | |

table continued on next page ...

ADMIN UPDATE #1: 2018-JAN-24

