The major toxic effects of durvalumab or tremelimumab which are anticipated to limit dosing are hypersensitivity/ infusion related reactions and possible class related immune related AEs, based on the mechanism of action of durvalumab ± tremelimumab leading to T-cell activation and proliferation. Potential immune related AEs include pneumonitis, hepatitis, diarrhea/colitis and intestinal perforation, endocrinopathies (hypo and hyperthyroidism, adrenal insufficiency, hypophysitis/hypopituitarism diabetes insipidus and Type 1 diabetes mellitus), nephritis, rash/dermatitis, pancreatitis, myocarditis, myositis/polymyositis and rare/less frequent irAEs including neuromuscular toxicities such as myasthenia gravis and Guillain-Barre syndrome. Other inflammatory responses that are rare with a potential immune-mediated etiology include, but are not limited to, pericarditis, sarcoidosis, uveitis and other events involving the eye, skin, hematological and rheumatological events. It is possible that events with an inflammatory or immune mediated mechanism could occur in nearly all organs. With anti-PD-L1 and anti-CTLA-4 combination therapy, the occurrence of overlapping or increasing cumulative toxicities that include immune related AEs could potentially occur at higher frequencies than with either durvalumab or tremelimumab monotherapy.

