9.1.1 Durvalumab +/- Tremelimumab Adverse Events of Special Interest

An adverse event of special interest (AESI) is one of scientific and medical interest specific to understanding of the Investigational Product and may require close monitoring. An AESI may be serious or non-serious.

AESIs for durvalumab ± tremelimumab include, but are not limited to events with a potential inflammatory or immune-mediated mechanism and which may require more frequent monitoring and/or interventions such as steroids, immunosuppressants and/or hormone replacement therapy. **These AESIs may require close monitoring in the treatment arms with durvalumab ± tremelimumab.**

An immune-mediated adverse event (imAE) is defined as an AESI that is associated with drug exposure and is consistent with an immune-mediated mechanism of action and where there is no clear alternate etiology. Serologic, immunologic, and histologic (biopsy) data, as appropriate, should be used to support an imAE diagnosis. Appropriate efforts should be made to rule out neoplastic, infectious, metabolic, toxin, or other etiologic causes of the imAE.

If the Investigator has any questions in regards to an event being an imAE, the Investigator should promptly contact the CCTG.

AESIs observed with durvalumab ± tremelimumab include:

- Diarrhea / Colitis, and intestinal perforation;
- Pneumonitis / Interstitial Lung Disease (ILD);
- ALT/AST increases / hepatitis / hepatotoxicity;
- Neuropathy / neuromuscular toxicities (e.g. Guillain-Barré syndrome, and myasthenia gravis);
- Endocrinopathies (i.e. events of hypophysitis, hypopituitarism, adrenal insufficiency, diabetes insipidus, hyper- and hypothyroidism and type I diabetes mellitus);
- Rash / Dermatitis;
- Nephritis / Blood creatinine increases;
- Pancreatitis (or labs suggestive of pancreatitis - increased serum lipase , increased serum amylase);
- Myocarditis;
- Myositis/polymyositis
- Other inflammatory responses that are rare with a potential immune-mediated aetiology include, but are not limited to, pericarditis, sarcoidosis, uveitis and other events involving the eye, skin, hematological and rheumatological events.

In addition, infusion-related reactions and hypersensitivity/anaphylactic reactions with a different underlying pharmacological etiology are also considered AESIs.

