Dosing Modification and Toxicity Management Guidelines for Immune-Mediated, Infusion-Related, and Non-Immune-Mediated Reactions (MEDI4736 Monotherapy or Combination Therapy With Tremelimumab or Tremelimumab Monotherapy) 1 November 2017 Version

General Considerations

| Dose Modifications | Toxicity Management |
|---|--|
| 
Note: For Grade ≥ 3 asymptomatic amylase or lipase levels, hold study drug/study regimen, and if complete work up shows no evidence of pancreatitis, study drug/study regimen may be continued or resumed.
 
Note: Study drug/study regimen should be permanently discontinued in Grade 3 events with high likelihood for morbidity and/or mortality – e.g., myocarditis, or other similar events even if they are not currently noted in the guidelines. Similarly, consider whether study drug/study regimen should be permanently discontinued in Grade 2 events with high likelihood for morbidity and/or mortality – e.g., myocarditis, or other similar events even if they are not currently noted in the guidelines – when they do not rapidly improve to Grade <1 upon treatment with systemic steroids and following full taper
 
Note: There are some exceptions to permanent discontinuation of study drug for Grade 4 events (i.e., hyperthyroidism, hypothyroidism, Type 1 diabetes mellitus).
 | 
not currently noted in the guidelines – when these events are not responding to systemic steroids.
 
With long-term steroid and other immunosuppressive use, consider need for Pneumocystis jirovecii pneumonia (PJP, formerly known as Pneumocystis carinii pneumonia) prophylaxis, gastrointestinal protection, and glucose monitoring.
 
Discontinuation of study drug/study regimen is not mandated for Grade 3/Grade 4 inflammatory reactions attributed to local tumor response (e.g., inflammatory reaction at sites of metastatic disease and lymph nodes). Continuation of study drug/study regimen in this situation should be based upon a benefit-risk analysis for that patient.
 |

AE Adverse event; CTC Common Toxicity Criteria; CTCAE Common Terminology Criteria for Adverse Events; im/AE immune-mediated adverse event; IV intravenous; NCI National Cancer Institute; PO By mouth.

Pediatric Considerations

| Dose Modifications | Toxicity Management |
|--|--|

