7.4.6 Baseline Exams

- Baseline signs and symptoms (**Table 14**)
- Baseline hematology: WBC, neutrophils, platelets, hemoglobin, RBC, lymphocytes, monocytes, eosinophils, basophils (**Table 15**)
- Baseline serum chemistry: Total bilirubin, AST, ALT, alkaline phosphatase, LDH, serum creatinine, chloride, sodium, albumin, potassium, calcium, magnesium, ALP, glucose, amylase, lipase, CEA (**Table 16**)
- Baseline Thyroid Function Tests (**Table 17**)
- Baseline Coagulation Tests (**Table 18**)
- Baseline ECG (**Table 19**)
- Baseline urinalysis (**Table 20**)

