7.7.2 Laboratory Evaluations

For patients on Durva+Treme, laboratory evaluations reported on Treatment Report or 4-Week Post-Treatment Follow-Up Report for patients on the Durva+Treme arm will be included in the calculation for laboratory adverse events on Durva+Treme. All laboratory evaluations reported after baseline assessment will be included in the calculation for overall laboratory adverse events. Laboratory results will be classified according to CTCAE version 4.0. Laboratory tests that are not covered by the CTCAE grading system will be summarized according to the following categories: normal and above the upper normal limits.

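### Glucose is graded at baseline but is the only chemistry analyte missing from both post-baseline laboratory lists and from Tables 49 and 50 of the SAP

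*SAP*

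**What the plan says.** **SAP, baseline.** Section 7.4.6 includes glucose in the serum chemistry list: "calcium, magnesium, ALP, glucose, amylase, lipase, CEA". Table 16 gives it two blocks, hyperglycaemia and hypoglycaemia, each with grades 0 to 4 and a line for values not reported, by arm and in total.

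**SAP, after baseline.** Section 7.6.2.2 has one list for the period on durvalumab and tremelimumab (Table 49) and one for the whole study in both arms (Table 50). The first ends "serum creatinine, chloride, sodium, albumin, potassium, calcium, magnesium, ALP, amylase, lipase, CEA on Durva+Treme". The second repeats the same analytes. Neither names glucose, and neither table shell has a glucose row.

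**SAP, general rule.** Section 7.7.2 states: "All laboratory evaluations reported after baseline assessment will be included in the calculation for overall laboratory adverse events".

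**Protocol, collection.** The flowsheets in 5.1 and 5.2 both show "Glucose | X | as clinically indicated": once before the study, then on demand. Glucose is outside the biochemistry panel that is drawn every 4 weeks in Arm 1 and on Day 1 of each cycle in Arm 2.

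**Protocol, risk.** Section 7.1.1 names type 1 diabetes among the potential immune-related events ("hypophysitis/hypopituitarism diabetes insipidus and Type 1 diabetes mellitus"), and 9.1.1 lists it among the events of special interest ("adrenal insufficiency, diabetes insipidus, hyper- and hypothyroidism and type I diabetes mellitus"). Appendix III, General Considerations, asks investigators to consider "gastrointestinal protection, and glucose monitoring" with long-term steroid use.

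**Protocol, recording.** Section 9.1.2 says that laboratory abnormalities on protocol specified tests are not recorded as adverse events, because they are derived electronically from the submitted values.

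**The concern.** The laboratory marker of a named event of special interest is graded at baseline and then has no place in the post-baseline laboratory output. Any glucose value collected after baseline would fall under the inclusion rule in SAP 7.7.2, yet no list or shell would show it. The report could then give neither a worst post-baseline grade to set against Table 16 nor a description of the two arms side by side, even for patients with values on file.

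Protocol 9.1.2 makes this more than a formatting slip. It relies on the laboratory tables to carry abnormalities that are kept out of the adverse event record. A test that falls under that rule but has no laboratory row can drop out of the safety report altogether. Safety is a secondary objective (Protocol 1.2), and SAP 4.3 names laboratory parameters among the safety endpoints.

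**Working it through.** No sample-size or error-rate figure is involved. The check compares the lists and the table shells.

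**1. Lists.** Entries are counted as printed.

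| SAP list | Entries | Glucose |
|---|---|---|
| 7.4.6, baseline | 17 | yes |
| 7.6.2.2, on treatment | 16 | no |
| 7.6.2.2, overall | 16 | no |

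Baseline minus post-baseline leaves one entry, glucose. Post-baseline minus baseline leaves none. Alkaline phosphatase appears in every list both in full and as ALP. Counting it once gives 17 − 1 = 16 and 16 − 1 = 15, and the difference is still glucose.

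**2. Shells.** Glucose blocks: Table 16 has 2, Table 49 has 0, Table 50 has 0. Every other analyte in Table 16 has a counterpart in both later tables, so the shells agree with the lists.

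**3. Does on-demand testing explain the gap?** The scheduled biochemistry row in Protocol 5.1 and 5.2 names 16 analytes. TSH goes to the thyroid tables, and 16 − 1 = 15 matches the 15 distinct post-baseline analytes in step 1. So the list follows the scheduled panel. The SAP does not, however, confine its tables to scheduled tests:

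- ECG is on demand after baseline (Protocol 5.1 and 5.2; SAP 7.6.3.1) and has Table 55.
- Urinalysis is described as on demand (SAP 7.6.3.2) and has Table 56.
- T3 and T4 are measured only if TSH is abnormal (flowsheet footnotes) and have Tables 51 and 52.

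**4. Could another output show it?**

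- *Adverse event tables 42 to 46.* Diagnosed type 1 diabetes recorded as an adverse event would appear here, in Tables 43 and 46 only if grade 3 or higher. A glucose abnormality without a diagnosis would be kept out if glucose counts as a protocol specified test under 9.1.2. It could be recorded if glucose does not.
- *Table 58.* This covers adverse events that end treatment. Appendix III allows isolated type 1 diabetes to be managed without interrupting study drug, so such a case need not reach this table.
- *Table 56.* The protocol's dipstick includes glucose, but the shell has no row identified as glucose.

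**5. Denominator.** Table 16 has a line for values not reported. Tables 49 and 50 have neither that line nor a grade 0 line, so a glucose block copied in their format would not show how many patients were tested.

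**The case against.** The strongest reply has four parts.

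*The main clinical risk is not lost.* A reader might infer that type 1 diabetes would leave no trace in the report. The documents do not support that. It is a diagnosis, Appendix III manages it as a graded immune-mediated event, and 9.1.2 excludes laboratory abnormalities, not diagnoses. This part stands in full and limits the point to laboratory-only findings.

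*The protocol does not contradict itself.* A reader might set on-demand glucose testing against the events of special interest in 9.1.1 and the glucose monitoring in Appendix III. But 9.1.1 says only that such events may need close monitoring. Appendix III ties glucose to a suspected endocrinopathy or to long-term steroids. Both are event-driven and fit the flowsheets. This part also stands. How often glucose is tested is a clinical decision for the sponsor, and the SAP records that randomization closed in June 2017.

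*It is not known that values exist.* SAP 7.7.2 covers reported evaluations, and the case report forms are not among the documents. Whether an unscheduled glucose counts as a protocol specified test is also unclear. Both are fair, so the consequence has to be stated conditionally.

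*The added rows would be selective.* Patients tested on demand are not a random subset, and testing may differ by arm in an open-label trial. This is right and governs how the rows are labelled. It does not justify omitting them, since ECG, urinalysis and T3/T4 are tabulated despite similar selection.

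**Conclusion.** The omission is real and narrow: one analyte of 17, absent from two lists and two tables, with no reason given and against the SAP's own inclusion rule. It leaves any collected post-baseline glucose without a laboratory row. It could remove laboratory-only hyperglycaemia from both outputs, on two assumptions that the documents do not settle: that post-baseline glucose values reach the database, and that glucose counts as a protocol specified test under 9.1.2.

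The size in patients cannot be given. The documents state no rate of immune-mediated diabetes or of hyperglycaemia, so any count among the 120 patients planned for the combination arm would be a guess, and the finding does not depend on one. The primary endpoint and the secondary efficacy endpoints are unaffected. Severity: minor.

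**What to change.** - Add glucose to both lists in SAP 7.6.2.2.
- Add hyperglycaemia and hypoglycaemia rows, worst CTCAE grade per patient, to Tables 49 and 50. Table 16 supplies the layout.
- Use the number of patients with at least one post-baseline glucose value, shown per arm, as the denominator for these rows.
- Add a footnote that post-baseline glucose was tested only when clinically indicated, so the rates describe tested patients and any comparison between arms is descriptive.
- If the case report forms have no field for post-baseline glucose, say so in the SAP in place of the rows.

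The cost is one word in each list, two blocks in each of two tables, and a footnote. No new data are needed. No change to the glucose testing schedule is proposed.

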5.1 Patient Evaluation Flowsheet: Pre-study (Baseline) and Post-randomization Follow-up
For Patients Randomized to Best Supportive Care (Arm 1)

| Required Investigations | PRE-STUDY (≤ 14 days prior to randomization, unless otherwise indicated) | PRIOR to objective disease progression (timing from randomization) | | AFTER objective disease progression (timing from randomization) |
|---|---|---|--|--|
| | | Every 4 weeks until objective disease progression | Every 8 weeks until objective disease progression (maintain schedule even if clinic visits are delayed) ³ | Every 12 weeks |
| History and Physical Exam | | | | |
| Including: height (baseline only), weight, ECOG performance status, clinical tumour measurements (if applicable) | X | X | | |
| Vital Signs (blood pressure, heart rate, temperature) | X | X | | |
| Concomitant Medications | X | X | | |
| Overall Survival | | | | |
| Survival Status Assessment | | X | X | X ¹ |
| Hematology | | | | |
| CBC, differential (including lymphocytes), platelets | X | X | | |
| Coagulation | | | | |
| PTT, PT/INR | X | X | | |
| Biochemistry | | | | |
| Serum Creatinine, Chloride, Sodium, Potassium, Calcium, Magnesium, Bilirubin, ALP, AST and ALT, LDH, Albumin, TSH ² , Amylase, Lipase, Serum CEA | X | X | | |
| Creatinine Clearance (calculated) | X | as clinically indicated | | |
| Glucose | X | as clinically indicated | | |
| Radiology³ | | | | |
| Chest/abdomen/pelvis CT or MRI scan ³ | X ≤ 28 days | | X ³ | |
| Other scans as necessary to document all measurable and non-measurable disease ³ | X ≤ 28 days | | | |
| Other Investigations | | | | |
| Pregnancy Test ⁴ | X | | | |
| ECG | X | as clinically indicated | | |
| Dipstick Urinalysis (including protein, specific gravity, glucose and blood) | X | | | |

table continued on next page ...

| Correlative Studies | | | |
|--|--|---|--|
| Archival Tissue Sample ⁵ (mandatory) | Availability of sufficient tissue must be confirmed prior to randomization | Submit tissue within 4 weeks of randomization | |
| Whole blood, plasma and serum ^{5,6} (mandatory) | X | To be done at 8 weeks, and at the time of objective disease progression ⁷ , if not already done | |
| Adverse Events | | | |
| Adverse Event Assessment ⁸ | X (To document residual adverse events from previous therapy and baseline symptoms) | X To be evaluated continuously for adverse events (until objective disease progression) | |
| Quality of Life | | | |

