8.2 Response and Evaluation Endpoints

Response and progression will be evaluated in this study using the revised international criteria (1.1) proposed by the RECIST (Response Evaluation Criteria in Solid Tumours) committee as well as the Immune-Related Response Criteria (irRECIST). In the event of disease progression using the RECIST 1.1 criteria (unconfirmed PD (uPD)), investigators should continue treatment, if the patient is clinically stable (i.e. stable performance status and disease related symptoms) until disease progression is confirmed at a subsequent scan at least 4 weeks later (unequivocal confirmed disease progression (cPD)). This is particularly important for patients in whom pseudoprogression may have occurred. Follow up response assessments must be continued until unequivocal disease progression has occurred.

8.2.1 Measurable Disease.

Measurable *tumour lesions* are defined as those that can be accurately measured in at least one dimension (longest diameter to be recorded) as ≥ 20 mm with chest x-ray and as ≥ 10 mm with CT scan or clinical examination. Bone lesions are considered measurable only if assessed by CT scan and have an identifiable soft tissue component that meets these requirements (soft tissue component ≥ 10 mm by CT scan). *Malignant lymph nodes* must be ≥ 15 mm in the short axis to be considered measurable; only the short axis will be measured and followed. All tumour measurements must be recorded in millimetres (or decimal fractions of centimetres). Previously irradiated lesions are not considered measurable unless progression has been documented in the lesion.

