APPENDIX IV - DOCUMENTATION FOR STUDY

Follow-up is required for patients from the time of randomization and will apply to all eligible patients.

This trial will use a web-based Electronic Data Capture (EDC) system for all data collection. For details of accessing the EDC system and completing the on-line Case Report Forms please refer to the “CCTG EDC Generic Data Management Guidebook” posted on the CO.26 area of the CCTG web-site (www.ctg.queensu.ca).

The electronic CRFs to be used in this trial, through the EDC system, are as follows:

| Electronic Folder | Timing | To be completed electronically | Supporting Documentation Required ¹ |
|---|--|--|--|
| Eligibility Checklist | | At the time of randomization | 
 • consent form² |
| Baseline Report | | Within 2 weeks of randomization | 
 • relevant pathology report(s) • RAS reports • relevant operative report(s) • relevant radiology reports (including CT/MRI abdomen/pelvis, CT/MRI chest, chest x-ray) • tumour measurement worksheet • ECG report |
| Correlative Studies Report (Tumour and Blood) | Continuous running-log folder See Section 5.0 | Information pertaining to tumour tissue submission must be completed as soon as possible after randomization, and tissue submitted within 4 weeks of randomization. | 
 • Consent form² • Diagnostic pathology report (for tumour tissue only) |
| | | Information pertaining to baseline/pretreatment blood collection for correlative studies (i.e. whole blood, plasma, serum) must be completed within 2 weeks of randomization. | |
| | | Information pertaining to post randomization blood collection samples (i.e. whole blood, plasma, serum) for correlative studies and banking should be completed within 2 weeks after collection of blood specimens. | |
| Concomitant Medication Report | Continuous running-log folder | | |
| Best Supportive Care Report (Arm 1 only) | Every 4 weeks (28 days) until objective progression | Within 2 weeks of the end of each reporting period | 
 • If available/applicable: • CT/MRI abdomen/pelvis report • CT/MRI chest • other radiology reports • tumour measurement worksheet • ECG report |

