| Treatment Report (Arm 2 only) | Every 4 weeks (28 days) while patient is on protocol treatment | Within 2 weeks of the end of each 4 week reporting period | If available/applicable: 
 • CT/MRI abdomen/pelvis report • CT/MRI chest • other radiology reports • tumour measurement worksheet • ECG report |

table continues on next page ...

| Electronic Folder | Timing | To be completed electronically | Supporting Documentation Required ¹ |
|--|---|---|--|
| End of Treatment Report(Arm 2 only) | As soon as permanent off treatment status is confirmed. | Within 2 weeks of end of treatment | |
| 4-Week Post-Treatment Follow-Up Report (Arm 2 only) | 4 weeks from the date of last infusion | Within 2 weeks of the 4-week post treatment follow up visit | 
 • relevant radiology reports |
| Follow-up Report ³ (Arm 2 only) | Every 4 weeks (28 days) until objective progression | Within 2 weeks of follow-up visit | If available/applicable: 
 • CT/MRI abdomen/pelvis report • tumour measurement worksheet • CT/MRI chest report • other radiology reports • ECG report |
| Short Follow-up Report | Every 12 weeks after objective disease progression | Within 2 weeks of follow-up visit | |
| Relapse/Progression Report | Upon the patient's objective disease progression / relapse | Within 4 weeks of confirmation | 
 • relevant radiology, operative and pathology reports |
| Death Report | Upon patient's death | Within 4 weeks of patient death | 
 • autopsy/post-mortem report, if performed |
| Serious Adverse Event (SAE) Report ⁴ | Within 24 hours of event At time of event and reported to CCTG | Within 1 working day ⁴ | |
| Minimal Follow-up Report ⁵ | Annual | Within 6 weeks of contact | If available/applicable: 
 • autopsy report • CT/MRI report |

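### Table 50 sets worst chemistry grades side by side by arm over unequal observation windows, because BSC tests stop at progression and Arm 2 tests can run past it

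*SAP*

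**What the plan says.** SAP 7.7.2 sets the counting rule: "All laboratory evaluations reported after baseline assessment will be included in the calculation for overall laboratory adverse events". SAP 7.6.2.2 applies it to chemistry in both arms as overall "total bilirubin, AST, ALT, alkaline phosphatase, LDH, serum creatinine, chloride, sodium, albumin, potassium, calcium, magnesium, ALP, amylase, lipase, CEA: worst CTC grade per patient". The Table 50 shell puts DURVA+TREME and BSC in adjacent columns and has no p-value column. Tables 48 (hematology), 52 (thyroid) and 54 (coagulation) are built on the same rule.

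The protocol schedules the two arms differently.

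- **BSC.** Protocol 5.1 places biochemistry under "Every 4 weeks until objective disease progression" and leaves the after-progression cell blank. Appendix IV gives the Best Supportive Care Report the same end: "Every 4 weeks (28 days) until objective progression".
- **Arm 2, on treatment.** Protocol 5.2 schedules biochemistry on "Day 1 each cycle, and as clinically indicated". After a first RECIST 1.1 progression, Protocol 8.2 says "investigators should continue treatment, if the patient is clinically stable", until a later scan confirms it; Protocol 7.1.7 also allows this. The Treatment Report runs "Every 4 weeks (28 days) while patient is on protocol treatment".
- **Arm 2, after treatment.** Protocol 5.2 marks biochemistry at a visit "4 weeks after end of last cycle date", including for patients who have progressed. Footnote 5 limits testing after progression to patients with ongoing treatment-related hematologic AEs. Its superscript is on the 12-weekly cell and also on the Biochemistry row heading.
- **Arm 2, liver tests.** Appendix III asks for liver tests about every 1 to 2 days after a Grade 2 elevation. The BSC flowsheet has no counterpart.

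**The concern.** A per-patient worst grade is a maximum, so extra samples can raise it but never lower it. A fair comparison of maxima needs similar sampling in both arms. Before progression the arms match, since both are tested every 4 weeks. After progression only Arm 2 can contribute scheduled values. Appendix III itself lists disease progression among the other causes of raised liver tests.

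Table 50 can therefore mix drug effect with liver deterioration from progressing cancer, and the reader would have no way to separate them. The SAP gives this table no common window, no restriction to scheduled samples, no sample count and no caveat. The matter deserves some attention because hepatotoxicity is an adverse event of special interest (Protocol 9.1.1), and abnormalities in protocol-specified tests are not recorded as adverse events (Protocol 9.1.2). The graded liver tests therefore appear by arm after baseline only here.

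**Working it through.** The plan gives no rate or sample count for Table 50, so there is no stated figure to reproduce. The check has two steps: count samples from the schedules, then see what unequal counts do to a worst-grade proportion when the risk per sample is the same in both arms.

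**Step 1: sample counts, for progression found at the week 8 scan**

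- BSC: weeks 4 and 8, so 2 samples.
- Arm 2, stopped at week 8 (last dose week 4): the post-treatment visit falls at week 8 on Appendix IV timing (4 weeks from last infusion) or at week 12 on flowsheet timing. This gives 2 or 3 samples.
- Arm 2, progression confirmed at week 12 (last dose week 8): visit at week 12 or 16, so 3 or 4 samples.
- Arm 2, confirmed at week 16 (last dose week 12): visit at week 16 or 20, so 4 or 5 samples.

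On this reading Arm 2 has 2 to 5 samples. The last one falls 0 to 8 weeks (Appendix IV) or 4 to 12 weeks (flowsheet) after progression. The higher count in each case assumes that blood is also drawn at the visit where treatment stops.

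Suppose instead that footnote 5 removes the post-treatment sample, and that blood is drawn only when a dose is given. A patient stopped at week 8 then has 1 sample (week 4), and one confirmed at week 16 has 3 (weeks 4, 8 and 12). The range is 1 to 3, and the last sample falls between 4 weeks before and 4 weeks after the BSC one.

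**Step 2: effect on the worst-grade proportion**

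The documents give no rates, so the per-sample risk p of reaching a given grade is assumed equal in both arms.

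- Independent samples: P(at least one) = 1 − (1 − p)^n.
- Within-patient correlation ρ (beta-binomial): a = p(1 − ρ)/ρ, b = (1 − p)(1 − ρ)/ρ, and P = 1 − product over i = 0 to n − 1 of (b + i)/(a + b + i).

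For p = 5% and ρ = 0: n = 2 gives 1 − 0.95² = 9.8%, and n = 4 gives 1 − 0.95⁴ = 18.5%.

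For p = 5% and ρ = 0.3: a = 0.1167 and b = 2.2167. Then n = 1 gives 5.0%; n = 2 gives 1 − 0.95 × 3.2167/3.3333 = 8.3%; n = 3 gives 10.8%; n = 4 gives 12.7%.

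| Arm 2 samples (BSC always 2), p = 5% | ρ | Arm 2 | BSC |
|---|---|---|---|
| All with 4 | 0 | 18.5% | 9.8% |
| All with 4 | 0.3 | 12.7% | 8.3% |
| All with 4 | 0.6 | 8.9% | 6.9% |
| Half with 4, half with 2 | 0 | 14.1% | 9.8% |
| Half with 4, half with 2 | 0.3 | 10.5% | 8.3% |
| Half with 4, half with 2 | 0.6 | 7.9% | 6.9% |
| Half with 3, half with 1 (footnote 5 removes a sample) | 0.3 | 7.9% | 8.3% |

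Other per-sample risks, half of Arm 2 with 4 samples and ρ = 0.3: at 2%, (5.2 + 3.4)/2 = 4.3% v 3.4%; at 10%, (24.3 + 16.3)/2 = 20.3% v 16.3%. With equal sample counts the gap is zero in every case. A higher risk after progression is not modelled, since no rate is given; it would widen the gap wherever Arm 2 has post-progression samples.

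**The case against.** The strongest reply is that footnote 5 may remove the very sample that creates the imbalance. Because the superscript also sits on the row heading, it can be read as covering the post-treatment visit for progressed patients. On that reading, with few patients continuing, the last row of the table shows no Arm 2 excess. This stands: for scheduled tests the documents do not settle even the direction. It does not dispose of the point, because footnote 5 does not clearly stop Day 1 tests in patients still being dosed past progression, and those values are reported and counted.

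Four samples for all of Arm 2 is also near the top of the range, since continuation is for clinically stable patients only. This too stands, so the 18.5% v 9.8% row is an upper illustration and not an expectation.

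Three stronger readings are tempting, but the documents do not carry them.

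- A reader might infer an inflated false-positive rate. SAP 7.7.1 names Fisher's exact test for overall adverse events; SAP 7.7.2 names no test for laboratory grades, and Table 50 has no p-value column.
- A reader might infer that the 1-to-2-day repeats add affected patients. They start only once Grade 2 is present, so they can move a patient to Grade 3 or 4 but cannot add one with Grade 2 or higher. The documents also do not say that all repeats reach the case report form.
- A reader might take Table 50 as the only controlled evidence on liver harm. Clinical hepatitis can still appear by arm in Tables 45 and 46.

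**Conclusion.** The point holds in a limited form. The counting rule in SAP 7.7.2 gives the two arms different observation windows, so Table 50 can show an Arm 2 excess of liver abnormalities that comes from post-progression disease or more sampling. It cannot be said that it will. The size depends on how footnote 5 is applied, how many patients are treated past progression, how strongly repeat tests correlate, and the true rates, none of which the documents give. At an assumed 5% per sample it runs from roughly none, through 10.5% v 8.3%, to 18.5% v 9.8%. Table 49 (Arm 2 only) makes no comparison and is not affected. Severity is minor: this is a descriptive safety table, and the plan ties no efficacy conclusion or stopping rule to it.

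**What to change.** Keep Table 50 as the all-data display, with a footnote that observation windows differ by arm. Add a by-arm version that counts scheduled samples only, up to first RECIST 1.1 objective progression in both arms. Print the number of samples and patient-weeks per arm beside it, because a cut at progression does not equalise sampling if PFS differs. Make the same cut in Tables 48, 52 and 54.

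The cost is one extra programmed version of each table. Protocol 9.1.2 indicates that actual laboratory values are already supplied, so no new visits, tests or patients are needed. The restricted version misses toxicity that appears after progression or only on unscheduled tests; for chemistry, Table 49 and the all-data Table 50 still show it.
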